#### 3- WHITE BLOOD CELLS

WBC < 3,000/mm^3

**Step 1:** dose reduction should be considered and the first dose reduction may be instituted at the discretion of the Investigator.

**Step 2:** if the white count remains below 3,000/mm^3 despite the initial dose reduction, a further dose reduction may be implemented per the table below.

WBC < 1,500/mm^3: dose interruption will be mandatory.

Once WBC returns to 1,500/mm^3 for 3 days, everolimus may be restarted at the lowest (one tablet b.i.d) level. If the WBC is stable at the reduced dose for 3 days, everolimus may be increased to the next higher dose. Once WBC returns to levels > 3,000/mm^3 for 7 days, everolimus may be increased to the full dose.

#### **4- CHOLESTEROL**

Cholesterol > 300 mg/dL or > 8 mmol/L:

Dietary instruction is strongly recommended and statin therapy, e.g. fluvastatin, should be considered.

**If the abnormality persists, the dosing of everolimus will be adjusted as follows:**

Cholesterol > 300 mg/dL or > 8 mmol/L: Dose reduction should be considered.

Cholesterol > 350 mg/dL or > 9 mmol/L: Everolimus should be interrupted.

#### **5- TRIGLYCERIDES**

Triglycerides > 575 mg/dL or > 6.5 mmol/L: Dietary instruction is strongly recommended and statin therapy should be considered.

**If the abnormality persists, the dosing of everolimus will be adjusted as follows:**

Triglycerides > 575 mg/dL or > 6.5 mmol/L: Dose reduction should be considered.

Triglycerides > 750 mg/dL or > 8.5 mmol/L: everolimus should be interrupted.

#### **Everolimus dose reduction**

	Platelet count (/mm  )	Hemoglobin (g/dL)	WBC count (/mm  )	Cholesterol (mmol/L)	Triglycerides (mmol/L)
Dose reduction	<75,000	<8	<3000	> 8	>6.5
Interruption	<30,000	<6	<1500	>9	>8.5

An investigator may interrupt temporarily or reduce, the dosage of the investigational drug (everolimus), if in his/her opinion this is clinically warranted.

#### **Dose reduction steps**

It is recommended to reduce the dosing from by one dosing step e.g. from 0.75 mg bid to 0.5 mg bid . The dosing should, however, always follow a bid schedule.

## 13.6 Appendix 6: Grading of acute liver allograft rejection

Rejection Activity Index (RAI)		
Criteria which can be used to score liver allograft biopsies with acute rejection, as defined by the World Gastroenterology Consensus Document.		
Category	Criteria	Score
Portal inflammation	Mostly lymphocytic inflammation involving, but not noticeably expanding, a minority of the triads	1
	Expansion of most or all of the triads, by a mixed infiltrate containing lymphocytes with occasional blasts, neutrophils and eosinophils	2
	Marked expansion of most or all of the triads by a mixed infiltrate containing numerous blast and eosinophils with inflammatory spillover into the periportal parenchyma	3
Bile duct inflammation / damage	A minority of the ducts are cuffed and infiltrated by inflammatory cells and show only mild reactive changes such as increased nuclear: cytoplasmic ratio of the epithelial cells	1
	Most or all of the ducts infiltrated by inflammatory cells. More than an occasional duct shows degenerative changes such as nuclear pleomorphism, disordered polarity and cytoplasmic vacuolization of the epithelium	2
	As above for 2, with most or all of the duct showing degenerative changes or focal luminal disruption	3
Venous endothelial inflammation	Subendothelial lymphocytic infiltration involving some, but not a majority of the portal and/or hepatic venules	1
	Subendothelial infiltration involving most or all of the portal and/or hepatic venules	2
	As above for 2, with moderate or severe perivenular inflammation that extends into the perivenular parenchyma and is associated with perivenular hepatocyte necrosis	3

Total RAI Score = /9

Reference: Banff Schema for Grading Liver Allograft Rejection: An International Consensus Document. Hepatology 1997;25(3):658-63.

Grading of acute liver allograft rejection	
Global assessment of rejection grade made on a review of the biopsy and after the diagnosis of rejection has been established	
Global assessment*	Criteria
Indeterminate	Portal inflammatory infiltrate that fails to meet the criteria for the diagnosis of acute rejection (see reference below)
Mild	Rejection infiltrate in a minority of the triads that is generally mild and confined within the portal spaces
Moderate	Rejection infiltrate expanding most or all of the triads
Severe	As above for moderate with spillover into periportal areas and moderate to severe perivenular inflammation that extends into the hepatic parenchyma and is associated with perivenular hepatocyte necrosis

\*Verbal description of mild, moderate or severe acute rejection could also be labeled as Grade 1, 11, and 111, respectively.

Reference: Banff Schema for Grading Liver Allograft Rejection: An International Consensus Document. Hepatology 1997;25(3):658-63.

## 13.7 Appendix 7: Definitions of CMV disease in solid organ transplant recipients

Disease type	Probable	Definite
CMV syndrome	One or more of the following: 1. Fever >38°C for at least 2 days 2. New or increased malaise 3. Leukopenia 4. ≥5% atypical lymphocytes 5. Thrombocytopenia 6. Elevation of hepatic transaminases (ALT or AST) to 2 x upper limit of normal (applicable to nonliver transplant recipients) plus evidence of CMV in blood by viral culture, antigenemia or a DNA/RNA-based assay	Clinical and laboratory findings as in 'probable' case and no other cause of symptoms/signs identified
Pneumonia 	Signs and/or symptoms of pulmonary disease in the absence of other documented cause plus evidence of CMV in blood and/or  bronchoalveolar lavage (BAL) fluid by viral culture, antigenemia or a DNA/RNA-based assay	Signs and/or symptoms of pulmonary disease plus detection of CMV in lung tissue by culture, immunohistochemical analysis or in situ hybridization  with or without evidence of CMV in blood or BAL fluid by viral culture, antigenemia (BAL) or a DNA/RNA-based assay
Gastrointestinal disease	Symptoms of upper or lower gastrointestinal disease plus macroscopic mucosal lesions on endoscopy plus evidence of CMV in blood or biopsy tissue by viral culture, antigenemia or an RNA/DNA-based assay	Symptoms or signs of upper or lower gastrointestinal disease plus detection of CMV in gastrointestinal tissue by culture, immunohistochemical analysis or in situ hybridization 
Hepatitis	Elevation of bilirubin and/or hepatic enzymes in the absence of other documented cause of hepatitis  plus evidence of CMV in blood by anti-genemia or a DNA/RNA-based assay	Elevation of bilirubin and/or hepatic enzymes plus detection of CMV in liver tissue by culture, immunohistochemical analysis or in situ hybridization 
CNS disease	CNS symptoms in the absence of other documented cause plus evidence for CMV in CSF samples by viral culture or DNA-based assay	CNS symptoms plus detection of CMV in CNS tissue by culture, immuno-histochemical analysis or in situ hybridization 
Retinitis	Not applicable	Lesions typical of CMV retinitis must be confirmed by an ophthalmologist Symptoms/signs of organ dysfunction plus detection of CMV in affected tissue by culture, immunohistochemical analysis or in situ hybridization 
Other tissue invasive disease (nephritis, cystitis, myocarditis, pancreatitis, etc.)	Evidence of organ dysfunction in the absence of other documented cause  plus evidence of CMV in blood by viral culture, antigenemia or DNA/RNA-based assay	

Superinfection or coinfection with other pathogens may occur and should be noted when present.

If affected organ is the allograft, acute rejection must be excluded as a cause for the clinical symptoms.

The detection of CMV in both BAL and peripheral blood strengthens the evidence for probable CMV pneumonitis.

Although, immunohistochemistry and *in situ* hybridization techniques are more sensitive for the detection of CMV-infected cells than morphologic examination, the presence of typical cytomegalovirus inclusions should be considered evidence of definite disease.

## 13.8 Appendix 8: Milan Criteria

The United Network of Organ Sharing (UNOS) decided to prioritize allocation of organs to those HCC patients who met the tumor criteria recognized in the Milan experience to have the best outcomes (TNM = T2N0). The Milan criteria are based on tumor burden and limit prioritization for OLT to those who have either a single tumor under 5 cm or those with 3 or less tumors each under 3 cm, without evidence of metastatic disease or vascular invasion. The Milan criteria provide a simple means of selecting patients with HCC for transplantation who are at low risk (~10%) for recurrence.

### Modified Tumor Node Metastases (pTNM) Classification of HCC

pT0	Tumor not found
pT1	1 nodule $\leq$ 1.9 cm
pT2	1 nodule 2.0 – 5.0 cm; 2 or 3 nodules, all $\leq$ 3.0 cm
pT3	1 nodule $>$ 5.0 cm; 2 or 3 nodules, at least one $>$ 3.0 cm
pT4a	4 or more nodules, any size
pT4b	pT2, pT3 or pT4 plus gross intraphepatic portal or hepatic vein involvement as indicated by CT, MRI, or US
N1	Regional (portal hepatitis) nodes, involved
M1	Metastatic disease, including extrahepatic portal or hepatic vein involvement
Stage I	T1
Stage II	T2
Stage III	T3
Stage IVA1	T4a
Stage IVA2	T4b
Stage IVB	Any N1, any M1

### 13.9 Appendix 9: Histological grading and staging of chronic hepatitis – Ishak-Knodell

#### Modified HAI grading: necroinflammatory scores

	Score
A. Periportal or periseptal interface hepatitis (piecemeal necrosis)	
Absent	0
Mild (focal, few portal areas)	1
Mild/moderate (focal, most portal areas)	2
Moderate (continuous around < 50% of tracts or septa)	3
Severe (continuous around > 50% of tracts or septa)	4
B. Confluent necrosis	
Absent	0
Focal confluent necrosis	1
Zone 3 necrosis in some areas	2
Zone 3 necrosis in most areas	3
Zone 3 necrosis + occasional portal-central (P-C) bridging	4
Panacinar or multiacinar necrosis	6
C. Focal (spotty) lytic necrosis, apoptosis and focal inflammation*	
Absent	0
One focus or less per 10 x objective	1
Two to four foci per 10 x objective	2
Five to ten foci per 10 x objective	3
More than ten foci per 10 x objective	4
D. Portal inflammation	
None	0
Mild, some or all portal areas	1
Moderate, some or all portal areas	2
Moderate/marked, all portal areas	3
Marked, all portal areas	4

\* Does not include diffuse sinusoidal infiltration by inflammatory cells

Maximum possible score for grading 18

#### *Additional features which should be noted but not scored:*

Bile-duct inflammation and damage  
Lymphoid follicles  
Steatosis, mild, moderate or marked  
Hepatocellular dysplasia, large-or small cell  
Adenomatous hyperplasia  
Iron or copper overload  
Intracellular inclusions (e.g. PAS-positive globules, Mallory bodies)

#### *Immunohistochemical findings*

Information on viral antigens, lymphocyte subsets or other features, when available, should be recorded and may be semi-quantitatively expressed.

**Histological staging of chronic hepatitis – Ishak-Knodell**

Modified staging: architectural changes, fibrosis and cirrhosis

Change	Score
No fibrosis	0
Fibrous expansion of some portal areas, with or without short fibrous septa	1
Fibrous expansion of most portal areas, with or without short fibrous septa	2
Fibrous expansion of most portal areas with occasional portal to portal (P-P) bridging	3
Fibrous expansion of portal areas with marked bridging (portal to portal (P-P) as well as portal to central (P-C)	4
Marked bridging (P-P and/o P-C) with occasional nodules (incomplete cirrhosis)	5
Cirrhosis, probable or definite	6
Maximum possible score	6

*Additional features which should be noted but not scored:*

Intra-acinar fibrosis, perivenular ("chicken wire" fibrosis). Phlebosclerosis of terminal hepatic venules.

### Document History – Changes compared to previous final version of SAP

Date	Time point	Reason for update	Outcome for update	Section and title impacted (Current)
06NOV2017	Prior to - DB lock		N/A - First version	NA

## List of abbreviations

AE	Adverse event
ALT	Alanine Transaminase
ANCOVA	Analysis of Covariance
AST	Aspartate Transaminase
BPAR	Biopsy Proven Acute Rejection
CKD-EPI	Chronic Kidney Disease – Epidemiology Collaboration
CMV	Cytomegalovirus
CRO	Contract Research Organisations
DSMB	Data Safety Monitoring Board
DOR	Drop-Out Rate
FAS	Full Analysis Set
eGFR	Estimated Glomerular Filtration Rate
EVR	Everolimus
gamma GT	Gamma Glutamyltransferase
GFR	Glomerular Filtration Rate
HCC	Hepatocellular Carcinoma
HCV	Hepatitis C Virus
LCMS	Liquid Chromatography coupled with Mass Spectrometry
LTx	Liver Transplantation
LOCF	Last Observation Carried Forward
MDRD-4	Modification of Diet in Renal Disease, 4-variable version
MedDRA	Medical Dictionary for Drug Regulatory Affairs
MELD	Model of End Stage Liver Disease
MMRM	Mixed Model for Repeated Measures
PCP	Pneumocystis Carinii Pneumonia
PPS	Per-Protocol Set
RAP	Report and Analysis Process
RNA	Ribonucleic Acid
SAE	Serious Adverse Event
SAP	Statistical Analysis Plan
SOC	System Organ Class
TAC	Tacrolimus
TFLs	Tables, Figures, Listings
ULN	Upper Limit Normal Range
VAP	Validation Analysis Plan
WHO	World Health Organization

## 1 Introduction

This Statistical Analysis Plan (SAP) describes the implementation of the statistical analysis planned in the protocol.

### 1.1 Study design

This study was designed to provide data on efficacy and safety of a post-transplantation regimen in liver allograft patients consisting of reduced tacrolimus in the presence of everolimus.

This is a 12-month, multi-center, open-label, randomized, controlled study to evaluate efficacy and safety and evolution of renal function of everolimus (EVR) in co-exposure with tacrolimus (TAC) in de novo liver transplant recipients.

The trial tests the null hypothesis that there was no difference in renal function, estimated by eGFR according to the MDRD-4 formula, at 12 months after randomization between the everolimus-based tacrolimus-minimization regimen and the tacrolimus-based control regimen versus the alternative hypothesis that the difference is 7.0 ml/min/1.73m^2. A sample size of 105 in each group has 80% power to detect a difference in means of 7.0 ml/min/1.73m^2 assuming that the common standard deviation was 18.0 ml/min/1.73m^2 with a 5% two-sided significance level. (One will decide in favor of H1 when the difference in means would be 5.1 ml/min/1.73m^2 or greater in favor of the everolimus-based group.) To adjust the sample size for a common drop-out rate (DOR) of 20% (using the formula Nadj=N/(1-DOR)), 165 patients need to be randomized per group. Sample sizes were estimated using NQuery (Version 6.1) procedure “Two-group t-test for equal means (equal n’s)”.

At Baseline (Visit 2) between 7 and 21 days post LTx patients were assigned to one of the following two treatment groups in a ratio of 1:1.

- EVR/TAC group (ARM I):  
Everolimus (C0-h: 3-8 ng/mL\*) + tacrolimus (C0-h: < 5 ng/mL\*)
- TAC group (ARM II):  
Tacrolimus (C0-h: 6-10 ng/ml\*)

\*Trough levels as per local practice, e.g. liquid chromatography coupled with mass spectrometry (LCMS). Values derived from enzyme based assays were corrected (as described in the manufacturer's instructions).

No interim analysis was planned and performed.

An independent Data Safety Monitoring Board (DSMB) was instituted before study start. The DSMB reviewed safety-related issues in a meeting and were entitled to make recommendations for changes in study conduct. Details on the function of the DSMB and the frequency of the DSMB meetings was laid out in a separate DSMB Charter.

## 1.2 Analysis sets

The **Full Analysis Set** (FAS) consists of all patients as randomized that received at least one dose of study drug.

Following the intent-to-treat principle, patients will be analyzed according to the treatment they were assigned to at randomization.

The **Per-protocol Set** (PPS) consist of a subset of patients of the FAS who did not show major deviations from the protocol procedures that may have an impact on the study outcome. Reasons for exclusion of the Per-protocol Set may be (but are not limited to): deviations from entry criteria, errors in treatment assignment, use of excluded/forbidden/un-allowed medication, premature discontinuation of randomized treatment or study, poor compliance, loss to follow-up, missing data in the primary efficacy variable. Criteria that are assumed to have such an impact will be defined in the Protocol Deviations Module of the Validation and Planning (VAP) documentation, and assessed before database lock during the data review meeting.

The **Safety Set** will consist of all patients that received at least one dose of study drug and had at least one post-baseline safety assessment. Patients will be analyzed according to treatment received. Of note, the statement that a patient had no adverse events also constitutes a safety assessment.

## 1.3 Study objectives and endpoints

The primary objective was to demonstrate that an immunosuppressive regimen based on everolimus (EVR) in co-exposure with tacrolimus (TAC) has superior efficacy compared to tacrolimus alone on estimated glomerular filtration rate (MDRD-4 formula) at Month 12 in de novo liver transplant recipients.

The key secondary objective was to evaluate the incidence of a composite of treated biopsy proven acute rejection (BPAR), graft loss or death until Month 12.

Other efficacy related secondary objectives were

- To evaluate the incidence of a composite of treated BPAR, graft loss, death or loss to follow-up at months 6 and 12.
- To evaluate the incidence of each component of the composite efficacy endpoint at month at months 6 and 12.
- To evaluate the incidence of a composite of death or graft loss at months 6 and 12.
- To evaluate treated BPAR by: (1) incidence, (2) time to event, (3) severity, (4) final clinical diagnosis and outcome.
- To evaluate any acute rejection by: (1) incidence, (2) time to event, (3) severity(4) final clinical outcome outcome.
- To evaluate the incidence of:
  - Treated acute rejection.
  - BPAR.

- Treated BPAR

Other renal function related related secondary objectives were

- To evaluate the evolution of post-randomization renal function over time assessed by the change in estimated GFR (MDRD-4), including to Months 6, and 12.
- To evaluate renal function by eGFR using various methods (MDRD-4, Nankivell, Cockcroft-Gault, CKD-EPI and Hoek formulae).
- To evaluate the incidence of patients experiencing a decline in eGFR (MDRD-4) of < 10, 10<15, 15<20, 20<25, and  $\geq$  25 mL/min/1.73m^2 from Screening, Week 2 post transplantation (Day 15) and randomization to Months 6, and 12.
- To evaluate serum creatinine at various time points.
- To evaluate renal function and change in eGFR from screening, randomization, and Week 2 post transplantation (Day 15) to Months 6 and 12 eGFR in following subgroups: age (< 60 and  $\geq$  60 years), gender, race, renal function strata (< 30, 30<45, 45<60,  $\geq$  60 mL/min/1.73m^2, below/above 45 mL/min/1.73m^2, below/above 60 mL/min/1.73m^2), HCV status, lab MELD score categories ( $\leq$ 14, 15-19, 20-24, 25-29,  $\geq$  30), and diagnosis leading to transplantation.
- To evaluate urinary protein/creatinine ratio at various time points.
- To evaluate the incidence of proteinuria. as adverse event of special interest.
- To evaluate the incidence of and time to renal replacement therapy as concomitant therapy of special interest.

Safety related secondary objectives were

- To evaluate the incidence of Adverse Events (AEs)/Infections/Serious Adverse Events (SAEs).
- To evaluate the incidence of treatment-related side effects, including incidence of new onset diabetes mellitus (NODM), evolution of metabolic parameters as subdivisions of serum/plasma lipid panel, neurotoxicity and hypertension.
- To evaluate the incidence and reason (e.g. AE) of premature discontinuation of study medication and premature discontinuation from the study.
- To evaluate the incidence and reason (e.g. AE) of interruption and dose adjustment of study medication.

Virus (HCV, CMV) and Hepatocellular Carcinoma (HCC) related secondary objectives were

- To evaluate the incidence of HCV and HCV related fibrosis.
- To evaluate HCV viral load (HCV- messenger ribonucleic acid (mRNA) levels overall and by genotype).
- To evaluate incidence of and response to HCV antiviral treatment.

- To evaluate the rate of recurrence of HCC at 12 post-transplantation in patients with a diagnosis of HCC at the time of liver transplantation adjusting for various risk factors, such as number of tumor nodules, total tumor size and tumor metastasis.
- To evaluate the incidence of de novo HCC malignancies. (adverse event of special interest)
- • Incidence and severity of CMV viral infections.

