### **Renal function-related objectives**

[figure not shown]
- To evaluate the evolution of post-randomization renal function over time assessed by the change in estimated GFR (MDRD-4), including to Months 6, and 12.
- To evaluate renal function by eGFR using various methods (MDRD-4, Nankivell, Cockcroft-Gault, CKD-EPI and Hoek formulae).
- To evaluate the incidence of patients experiencing a decline in eGFR (MDRD-4) of  $< 10$ ,  $10-15$ ,  $15-20$ ,  $20-25$ , and  $\geq 25$  mL/min/1.73m^2 from Screening, Week 2 post transplantation and randomization to Months 6, and 12.
- To evaluate serum creatinine at various time points.
- To evaluate renal function and change in eGFR from screening, randomization, and Week 2 post transplantation to Months 6 and 12 eGFR in following subgroups: age ( $< 60$  and  $\geq 60$  years), gender, race, renal function strata ( $< 30$ ,  $30-45$ ,  $45-60$ ,  $\geq 60$  mL/min/1.73m^2, below/above 45 mL/min/1.73m^2, below/above 60 mL/min/1.73m^2), HCV status, lab MELD score categories ( $\leq 14$ ,  $15-19$ ,  $20-24$ ,  $25-29$ ,  $\geq 30$ ), and diagnosis leading to transplantation.
- To evaluate urinary protein/creatinine ratio at various time points.
- To evaluate the incidence of proteinuria of  $0.5-1.0$  g/day,  $1.0-3.0$  g/day and  $\geq 3.0$  g/day at various time points.
- To evaluate the incidence of and time to renal replacement therapy.

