## 4 Study design

This is a 12-month, multi-center, open-label, randomized, controlled study to evaluate efficacy and safety and evolution of renal function of everolimus (EVR) in co-exposure with tacrolimus (TAC) in *de novo* liver transplant recipients.

Patients will be consented and screened for eligibility prior to liver transplantation (LTx). The study treatment will start with a run-in period that ends on the day of randomization (RND), scheduled at 7-21 post- LTx. Patients after consent who have undergone successful LTx (with optional induction therapy) will be entered in this run in period (between 3 and 5 days post- LTx) and may be initiated on an optional induction therapy, MMF, TAC at investigators' discretion until at least day 7 or maximally until day 21 post LTx with mandatory CS therapy until at least Month 6 post Tx.

Patients on MMF according to local practice must have the MMF administration discontinued by the time of RND. MMF is discontinued according to local practice.

At day 7-21 post-transplantation the following information at minimum has to be obtained from a patient to be randomized into the study:

- Abbreviated MDRD eGFR > 30 mL/min/1.73m^2. Creatinine results obtained in local laboratory within 5 days prior to RND are acceptable.

All eligible patients (according to in-/exclusion criteria at RND) will be randomized in between 7 and 21 days post LTx to one of the two treatment groups in a 1:1 ratio:

**Arm 1: EVR/TAC group** (Tacrolimus minimization arm)

Everolimus should be initiated at the day of randomization. Therapeutic drug monitoring will be mandatory throughout the duration of the study. Whole blood trough levels should be obtained  $5 \pm 2$  days after either everolimus or tacrolimus doses are changed.

**Everolimus dosing:** Everolimus study drug will be started at the day of randomization at a dose of 1.0 mg b.i.d (2.0 mg daily dose). The everolimus whole blood trough (C-0h) levels should be targeted to be maintained between 3-8 ng/mL. The twice daily dose can be changed in order to maintain the 3-8 ng/mL C-0h levels through the remainder of the study.

**Tacrolimus dosing:** After everolimus whole blood trough levels have been confirmed to be in the target range (3-8 ng/mL), tacrolimus tapering should begin, achieving a target tacrolimus C-0h levels of <5 ng/mL plus corticosteroids by three weeks after randomization and continuing through the remainder of the study.

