**Arm 2: TAC group**

**Tacrolimus dosing:** Tacrolimus C-0h levels should be targeted to be maintained at 6-10 ng/mL plus corticosteroids.

Control assessments will be performed at day 8 and 15 and at month 1, 3, 6, 9, and 12 after randomization. The final examination will be performed at Month 12 after randomization and at timepoint of early discontinuation from study treatment, if applicable. Drug dosage will be modified regarding to C-0h level measured as per local practice at standard visits (target C-0h levels: Certican® 3-8 ng/mL; TAC <5 ng/mL in Arm I and TAC 6-10 ng/mL in Arm II). The established treatment will be continued until Month 12 post RND (final assessment). Renal function (eGFR) as well as efficacy (treated BPAR, graft loss, and/or death) will be assessed at every study visit.

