## 4 Change to protocol specified analyses

The study protocol was amended 5 times, the original protocol and all amendments are provided in [Appendix 16.1.1](#). Previous sections of this report describe the study conduct as amended. The key features of each amendment are given below:

**Amendment 1** (20-Jan2012), before generation of CRF and inclusion of first, introduced the following changes:

- Assessment schedule: Laboratory and GFR were shifted from Screening visit to baseline visit
- Additional assessment in Screening visit: Menopausal status and in all women of childbearing potential a pregnancy test

**Amendment 2** (26-Sep-2012), 15 patient had been randomized to the study. The major changes that were made to the protocol were as follows:

- Measurement of the Tacrolimus C-0h levels can now be performed as per local practice.
- Inclusion criteria – randomization 2 was rephrased for a clearer understanding.

- Inclusion criteria – randomization 3: AST and ALT levels were raised to  $\leq 5$  times ULN, evaluation of gamma GT was deleted due to the fact that it does not reflect a prognostically important mark.
- For a better understanding, exclusion criteria – randomization 2 was separated in 4 independent criteria. Platelet, neutrophil and white blood cell count was reduced to 50,000/mm^3, 1,000/mm^3 and 2,000/mm^3 respectively
- Former inclusion criteria – randomization 2 (now 6): Calculation mistake of concentration of hypertriglyceridemia was corrected.
- Graft loss was added as reason for premature patient withdrawal.
- Dispensing of study drug and instruction for use of study drug are described in more detail to avoid misuse.
- According to the adaptation of in- and exclusion criteria, the permission of study drug adjustment and interruption in case of inability of tolerance of the protocol-specific dosing scheme is described in more detail.
- PCP prophylaxis and treatment of oral candida will be performed according to local practice.
- It was added, that pregnancy outcomes must be collected for the female partners of any males who took study drug in this study

These amendments were not considered to have affected the interpretation of study results as they were minor.

**Amendment 3** (14-JUN2013): 57 patients had been randomized to the study:

Five sub-studies which will be conducted in selected centers were added to the protocol. In addition some editorial changes were performed.

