### **Efficacy-related objectives**

For the efficacy related events only the events between Visit 2 (Baseline) and Day 360 are relevant. That means, that all events outside before Baseline and after 360 are excluded from this analysis.

**Death:** All Cases documented on the following pages

- End of treatment
- Study completion

Date of event = Date of Death – Date of Baseline + 1

**Graft loss:** All cases documented on page Graft Loss

Date of event = Date of Graft loss – Date of Baseline + 1

**Acute rejection:** All rejections documented on page Liver Allograft Rejection with final clinical diagnosis “Acute rejection diagnosed by biopsy”, “Acute rejection diagnosed without biopsy” or “Acute and chronic rejection”.

Date of event = Date rejection was first suspected – Date of Baseline + 1

**Treated acute rejection:** All rejections documented on page Liver Allograft Rejection with [final clinical diagnosis “Acute rejection diagnosed by biopsy”, “Acute rejection diagnosed without biopsy” or “Acute and chronic rejection”] and anti-rejection therapy.

Date of event = Date rejection was first suspected – Date of Baseline + 1

**Biopsy proven acute rejection:** All rejections documented on page Liver Allograft Rejection with final clinical diagnosis “Acute rejection diagnosed by biopsy”.

Date of event = Date rejection was first suspected – Date of Baseline + 1

**Treated Biopsy proven acute rejection:** All rejections documented on page Liver Allograft Rejection with final clinical diagnosis “Acute rejection diagnosed by biopsy and anti-rejection therapy”.

Date of event = Date rejection was first suspected – Date of Baseline + 1

For **Kaplan-Meier analysis** the first occurred event will be used. If no event is treated the time will be censored at min (day of visit Month 12, 360). If visit Month was not performed, the last visit until Month 12 will be used.

Day of vist = Visit Date – Date of Baseline + 1

**Adverse of special interest** were defined as followed:

AE of special interest	Identification
HCV (Hepatitis C Virus)	PT „HEPATITIS C“ OR “HEPATITIS C VIRUS TEST POSITIVE” OR “CHRONIC HEPATITIS C” OR “ACUTE HEPATITIS C” OR “HEPATITIS C ANTIBODY” “HEPATITIS C ANTIBODY POSITIVE” “HEPATITIS C CORE ANTIBODY POSITIVE” PT contains “HEPATITIS C RNA” “HEPATITIS C VIRUS TEST” “HEPATITIS C VIRUS TEST POSITIVE”
HCV related fibrosis	PT “HEPATIC FIBROSIS” (Query: HCV related?)
CMV	HLT “CYTOMEGALOVIRAL INFECTIONS”
Proteinuria	SMQ “PROTEINURIA”

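### SAP 1.3 lists two reference points for secondary eGFR change that do not work as written: no Screening eGFR is scheduled, and the only scheduled Day 15 is two weeks after randomisation, not Week 2 after transplantation

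*SAP*

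**What the plan says.** The protocol (3.2, renal function objectives) counts patients with given falls in eGFR "from Screening, Week 2 post transplantation and randomization to Months 6, and 12". SAP 1.3 repeats this objective but adds a day number: "from Screening, Week 2 post transplantation (Day 15) and randomization to Months 6, and 12". It makes the same addition to the subgroup objective: "To evaluate renal function and change in eGFR from screening, randomization, and Week 2 post transplantation (Day 15) to Months 6 and 12 eGFR".

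The visit schedule in protocol section 4 counts days from randomisation: "Control assessments will be performed at day 8 and 15 and at month 1, 3, 6, 9, and 12 after randomization". Patients are "randomized in between 7 and 21 days post LTx", and for the investigational arm "Everolimus should be initiated at the day of randomization".

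On Screening, SAP section 4 summarises Amendment 1, made before the first patient was included: "Assessment schedule: Laboratory and GFR were shifted from Screening visit to baseline visit". The current protocol schedule agrees. In Table 2 the biochemistry and GFR rows begin at Visit 2.

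**The concern.** A change score means something only if its reference value is measured and is what its label says. Of the three references in SAP 1.3, one has no planned measurement. Another carries a label (Week 2 after transplantation) that disagrees with the only visit bearing its day number.

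A programmer working from SAP 1.3 would have to find unplanned pre-transplant creatinine values for the first and would probably use Visit 4 for the second. Change from Visit 4 starts after the regimens have begun to differ, so it is not a change from a pre-randomisation baseline. A reader shown only the Week 2 label could not tell.

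**Working it through.** The plan gives no figure of its own on this point, so the check is a comparison of schedules plus a day count.

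**1. Screening eGFR.** Protocol Table 2 marks neither haematology/biochemistry nor GFR at Visit 1. The itemised Visit 1 list in section 7 has viral serology, CMV and HCV monitoring and a pregnancy test, but no creatinine and no GFR. Both first appear in the Visit 2 list. Scheduled Screening eGFR values: 0. This rests on the current schedule; the Amendment 1 summary only explains how it arose.

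**2. Day 15.** Inputs:
- Randomisation is r days after transplantation, with r from 7 to 21 (protocol section 4).
- Visit 4 is Day 15, with Day 1 at randomisation (protocol Tables 4-1 and 2). The SAP's event-time rule in 5.5.2 counts the same way: "Visit Date – Date of Baseline + 1".
- The visit window is ±3 days up to Visit 5 (protocol section 7).

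Visit 4 in days after transplantation = r + 14. The date 14 days after transplantation, as a study day = 14 − r + 1.

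| r | Visit 4, days after transplantation | Study day of the date 14 days after transplantation |
|---|---|---|
| 7 | 21 | Day 8 (7 days after randomisation) |
| 14 | 28 | Day 1 (randomisation) |
| 15 | 29 | 0 (1 day before randomisation) |
| 21 | 35 | −6 (7 days before randomisation) |

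Visit 4 is therefore 21 to 35 days after transplantation, or 21 − 3 = 18 to 35 + 3 = 38 with the window. No patient has it in Week 2.

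On the other reading, with Day 15 counted from transplantation as day 1, the date is right but no visit is tied to it. It coincides with Visit 3 when r = 7 and with Visit 2 when r = 14. For other patients no nominal visit falls on it. It is after randomisation when r is below 14 and before it when r is above 14.

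**3. What change from Visit 4 estimates.** Let D12 and D15 be the between-group differences in mean eGFR at Month 12 and at Visit 4. The difference in mean change from Visit 4 is D12 − D15. The difference in mean change from Visit 2 has expectation D12, because randomisation makes the expected Visit 2 difference zero. The gap is D15. The documents plan for D12 = 7.0 mL/min/1.73m² and say nothing about D15.

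The dosing timetable shows that D15 need not be zero. Everolimus starts at randomisation and is meant to be in range within 14 days (protocol 6.6.2). Tacrolimus tapering follows confirmation of that level and is to reach target by three weeks (section 4).

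**4. Which text governs.**
- Protocol 10.5.1 takes the decline categories from baseline only.
- SAP 2.3.6 takes changes over the course of the study from baseline only.
- SAP 2.5.1 and 2.5.2, the renal methods, do not mention the decline categories. SAP 1.3 is thus the only place in the SAP that gives them reference points.
- SAP section 4 drops the HCV fibrosis-progression objective and redefines proteinuria, but does not mention these references.
- SAP 2.3.4 did make the parallel correction elsewhere. The covariate that protocol 10.4.2 calls eGFR at Visit 1 (Baseline) became eGFR at Visit 2.

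**The case against.** The best defence is that SAP 1.3 is a list of objectives. The analyses that are written out, in protocol 10.5.1 and SAP 2.3.6, use baseline. SAP 1.3.1 plans subgroup summaries of the primary variable, with strata defined at baseline. Randomisation is one of the three listed references, so the valid comparison is not lost. All of this stands, and it limits the harm. It does not remove the problem, because the SAP methods never take up the decline categories and section 4 does not retire the other two references.

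Second, the Table 4-1 footnote calls the day of transplantation day 1. On that numbering, Day 15 simply restates Week 2 after transplantation. This is a fair reading and cannot be excluded. It removes the mislabelling but leaves a reference with no visit tied to it, before randomisation for some patients and after it for others.

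A reader might also infer more than the documents support:

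- *That Screening eGFR does not exist.* Only its absence from the schedule is shown. SAP 1.3.1 says lab MELD was measured at screening, so some local laboratory values may be available.
- *That the SAP turned a pre-treatment reference into a treated one.* The protocol's own Week 2 already fell after randomisation for patients randomised early in the 7-to-21-day window.
- *That tacrolimus was already being tapered at Day 15.* Tapering waits for a confirmed everolimus level, so some patients may not have started.
- *That the effect would be understated by a stated percentage.* Assuming that 1 to 3 of the planned 7.0 mL/min/1.73m² had appeared by Day 15 would give 1/7 = 14% to 3/7 = 43%. Nothing in the documents supports that assumption, or even fixes the sign of an early difference.

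**Conclusion.** The point holds as a defect in the definition of secondary objectives. The Screening reference has no scheduled data. The Day 15 reference is either Visit 4 under a label that fits no patient (21 to 35 days after transplantation, post-randomisation), or a post-transplant date with no visit tied to it and an inconsistent position relative to randomisation. Both conclusions follow from the documents' own schedule and need no outside assumption.

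Change from Visit 4 would subtract whatever between-group difference existed by then; its size cannot be derived from the documents. The table shells are not among the documents, so whether a table was built on these references cannot be told.

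The reach is limited to secondary renal analyses that the plan itself calls exploratory. It would be wrong to read this as touching the main result: the primary ANCOVA uses Visit 2 eGFR as covariate, and the sample size does not depend on these references. The point is worth correcting because it is cheap to correct and hard for a reader of the results to detect.

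**What to change.** In SAP 1.3:

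1. Delete Screening as a reference for eGFR change and decline.
2. Delete the Week 2 (Day 15) reference, or relabel it as Visit 4, post-randomisation, for description only and without a between-group interpretation.
3. Name Visit 2 (Baseline) as the reference for all eGFR changes and decline categories, including those in subgroups, as protocol 10.5.1 and SAP 2.3.6 already do.
4. Add the decline categories to SAP 2.5.1 and 2.5.2, so that their reference is given in the methods.
5. Record in SAP section 4 that this departs from protocol objective 3.2, and why: no Screening eGFR was scheduled, and no visit is tied to Week 2 after transplantation.

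The cost is wording and one entry in the list of changes. No new data are needed and there are fewer tables to program. If a table from either reference has already been produced, it needs a corrected title and a footnote giving the visit used and its timing relative to randomisation.
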